The information contained in this clinical protocol is only available to the investigators, the Ethics Committee and relevant agencies for review. Without approval from the principal investigator (PI), no information shall be given to a third party irrelevant to this study.

Abstract

Protocol Title	Safety of Laparoscopic Resection for Gastrointestinal Stromal Tumor on Unfavorable Anatomic Site of Stomach: a multicenter prospective trial
Protocol Version	V1.6
PI	[name]
Research Centers	Renji Hospital affiliated to Shanghai Jiaotong University School of Medicine Nanfang Hospital, Southern Medical University Peking University Cancer Hospital Zhongshan Hospital, Fudan University The First Affiliated Hospital of Nanjing Medical University Fujian Medical University Union Hospital Peking University People's Hospital Ruijin Hospital affiliated to Shanghai Jiao Tong University School of Medicine Union Hospital, Tongji Medical College, Huazhong University of Science and Technology West China Hospital, Sichuan University The First Affiliated Hospital, Sun Yat-Sen University Liaoning Cancer Hospital and Institute Chinese PLA General Hospital
Indications	Patients with gastrointestinal stromal tumor (GIST) at stomach whose diameter is ≥ 2 cm and ≤ 5 cm at unfavorable anatomic sites. Note: Favorable anatomic sites are defined as greater curvature and anterior wall of stomach by Soft Tissue Sarcoma, NCCN Clinical Practice Guidelines in Oncology (version 2. 2020). Accordingly, the unfavorable anatomic sites are defined as all the anatomic locations of stomach except greater curvature and anterior wall, including less curvature, posterior wall, and area near pylorus or cardia.
Research Purpose	The aim of this trial is to evaluate the safety of laparoscopic resection for GIST whose diameter is ≥ 2 cm and ≤ 5 cm at unfavorable anatomic sites of stomach

Research Design	Prospective, multicenter, open-label, single-arm
Case Grouping	Study group: laparoscopic resection for GIST at unfavorable anatomic sites of stomach
Determination of Sample Size	
The reference group proportion is 0.9800 according to the 3-year disease free survival rate reported in the previous literature on the subject of gastric GIST with maximum diameter between 2 to 5cm. -0.06 is set to detect a non-inferiority margin. The test statistic used is the one-sided Z test (unpooled). The significance level of the test is 0.025. The target Power is 0.80. The inconsistency rate between preoperative and postoperative pathological diagnosis of GIST from literature is about 30%. The dropout rate during follow-up is assumed to be 10%. The sample size needed by the study group was 182.

Number of Research Centers	13
Inclusion Criteria	
Diagnosed as gastrointestinal stromal tumor at unfavorable anatomic sites of stomach preoperatively by endoscopy, ultrasound endoscopy, CT or MRI;
 
Diameter of tumor size is ≥ 2cm and ≤ 5cm confirmed by contrast CT or MRI;
 
Patients whose tumor is resectable by laparoscopic techniques at preoperative assessment;
 
No evidence of distant metastasis and tumor invading nearby organs at preoperative assessment;
 
Performance status of 0 or 1 on ECOG (Eastern Cooperative Oncology Group) scale;
 
ASA (American Society of Anesthesiology) score I, II, or III;
 
Written informed consent.

Exclusion Criteria	
Women during pregnancy or breast-feeding;
 
Severe mental disorder;
 
History of previous upper abdominal surgery (except laparoscopic cholecystectomy);
 
History of other malignant disease within the past five years;
 
History of previous neoadjuvant imatinib therapy;
 
History of unstable angina or myocardial infarction within the past six months
 
History of cerebrovascular accident within the past six months;
 
History of continuous systematic administration of corticosteroids within the past month;
 
Requirement of simultaneous surgery for other disease;
 
Emergency surgery due to complication (bleeding, obstruction or perforation);
 
FEV1 < 50% of predicted value.
 
Patients with GIST locates at favorable anatomic sites detected by contrast CT, MRI or ultrasound endoscopy at preoperative assessment;
 
Patients with GIST diameter < 2cm or >5cm detected by contrast CT or MRI;
 
Presence of distant metastasis or tumor invading nearby organs at preoperative assessment

Withdrawal Criteria	
Patients postoperatively confirmed as non-GIST case by pathology;
 
 ● GIST Patients diagnosed with GIST at unfavorable anatomic site preoperatively but confirmed at favorable anatomic site intraoperatively; ● Patients confirmed as spontaneous tumor rupture, metastasis or invading nearby organs intraoperately; ● Requirement of simultaneous surgery for other disease; 
Sudden severe complications during the perioperative period (intolerable

	
surgery or anesthesia), which renders it unsuitable or unfeasible to implement the study treatment protocol as scheduled;
 
Patients confirmed to require emergency surgery by attending physicians due to changes in the patient's condition after enrolled into this study;
 
Patients who voluntarily quit or discontinue treatment for personal reasons at any stage after enrolled in this study;
 
Treatment implemented is proven to violate study protocol.

Intervention	Laparoscopic resection for GIST at unfavorable anatomic site of stomach will be conducted
Endpoints	
Primary Endpoint:
 
3-year disease-free survival rate (DFS)
 
Second Endpoints:
 
Success rate of laparoscopic surgery
 
Rate of intraoperative complication
 
Rate of Postoperative complication
 
3-year overall survival rate (OS)
 
Postoperative recovery course

Statistical considerations	
Statistical software SAS (version 9.4) will be used for statistical analysis.
 
The efficacy will be tested for non-inferiority with historical comparison and the safety indicators adopts descriptive analysis. All statistical tests will be conducted by bilateral test. The test level with statistical significance is 0.05.
 
The interval estimation of parameters is 95% confidence interval. K-M survival analysis and Cox regression model will be used for analysis of survival time data. Central effect analysis: mixed-effect model for quantitative measures, CMH method for qualitative measures, and hierarchical logistic regression model for grade variables, survival time variables will be evaluated and adjusted using a Cox regression model. The central effect analysis and subgroup analysis will be carried out according to the specific situation. Interim analysis of this study will be carried out.

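### The only non-inferiority test named for 3-year DFS, an unpooled Z test at 0.025, would have a true one-sided error of about 4.5% to 6% against 0.92, and no method is assigned to the primary decision

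*Combined protocol and SAP*

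**What the plan says.** All the text is in the abstract of the combined protocol and SAP.

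- **Research Design row:** "Prospective, multicenter, open-label, single-arm". There is no concurrent control.
- **Determination of Sample Size row:** the reference 3-year DFS is 0.98, and for the margin "0.06 is set to detect a non-inferiority margin" (printed with a minus sign). On the test, the row reads "The test statistic used is the one-sided Z test (unpooled). The significance level of the test is 0.025". Power is set at 0.80. Losses are 30% for diagnoses not confirmed by pathology and 10% for dropout. The result is given as "The sample size needed by the study group was 182".
- **Endpoints row:** the primary endpoint is the 3-year DFS rate.
- **Statistical considerations row:** the primary comparison is described only by "The efficacy will be tested for non-inferiority with historical comparison and the safety indicators adopts descriptive analysis". Tests are two-sided at 0.05 and intervals are 95%, with no construction given. For time-to-event outcomes in general, the row says "K-M survival analysis and Cox regression model will be used for analysis of survival time data". It also announces an interim analysis, without saying what it tests.

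Together these imply a rule that is not printed: the lower limit of a two-sided 95% interval for 3-year DFS must exceed 0.92. The abstract does not say how that limit is built, whether the Z test is for planning only, or how patients lost before 3 years count if DFS is analysed as a proportion.

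**The concern.** With true DFS near 0.98, about 2 events are expected among 114 evaluable patients (114 x 0.02 = 2.3), so one event can change the verdict. A Wald test takes its variance from the observed rate. When that rate is close to 1 the standard error is too small, and the lower limit sits too high. A reader who follows the one named test would therefore run the primary comparison above its own stated error rate. A reader who follows the K-M sentence still has to choose an interval type, and untransformed limits have the same defect. At stake is a claim of non-inferiority while a valid 95% interval still includes DFS below 92%.

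**Working it through.** **Inputs.** Reference 0.98, margin 0.06, one-sided 0.025, power 0.80, losses 30% and 10%, enrolment 182 (all from the Determination of Sample Size row). Threshold: 0.98 - 0.06 = 0.92. Assumption: the true rate used for power equals the reference, 0.98.

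**Step 1: the plan's own 182.**
- One-sample Z: (1.96 + 0.842)² x 0.98 x 0.02 / 0.06² = 42.7, so 43 evaluable. 43 / (0.7 x 0.9) = 68.3, so 69 enrolled.
- Two-sample Z, equal groups: twice that, 85.5, so 86. 86 / 0.63 = 136.5, so 137 enrolled.

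Neither gives 182, so the sample-size row does not settle which test is meant.

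**Step 2: evaluable patients at 182.** 182 x 0.7 x 0.9 = 114.7; 114 is used below.

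**Step 3: lower 95% limits at n = 114.** Wald: p - 1.96 x sqrt(p(1 - p)/n), where p is the observed event-free proportion. Exact: Clopper-Pearson.

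| Events | Wald | Exact |
|---|---|---|
| 3 | 0.944 (pass) | 0.925 (pass) |
| 4 | 0.931 (pass) | 0.913 (fail) |
| 5 | 0.919 (fail) | 0.901 (fail) |

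Wald passes with at most 4 events, exact with at most 3.

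**Step 4: true error and power at n = 114, X = number of events.**
- Wald: P(X ≤ 4 | 0.08) = 0.0446; power P(X ≤ 4 | 0.02) = 0.921.
- Exact: P(X ≤ 3 | 0.08) = 0.0162; power P(X ≤ 3 | 0.02) = 0.805.

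**Step 5: averaged over n ~ Binomial(182, 0.63).**

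| Rule | Error at DFS 0.92 | Power at DFS 0.98 |
|---|---|---|
| Wald | 6.1% | 94.2% |
| Exact | 1.5% | 79.1% |

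For every n from 80 to 182 the Wald error is above 2.5% (3.9% to 10.9%); the exact error is 0.6% to 2.5%. The two verdicts differ in 15% of trials at true DFS 0.98, 21% at 0.95 and 4.6% at 0.92.

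**Step 6: K-M at 3 years.** Simulation with confirmed GIST ~ Binomial(182, 0.7) and assumed exponential events and dropout (10% by 3 years). Untransformed Greenwood limits have an error of about 6%. Complementary log-log limits have an error of about 1% and power of about 77%. The two verdicts differ in about 19%, 26% and 5% of trials at DFS 0.98, 0.95 and 0.92.

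**Step 7: two-sample reading.** If "unpooled" meant a comparison with a reference sample whose rate is 0.98, the error depends on that sample's size, which the documents do not give. For assumed sizes of 50 to 1000 and n of 100 to 130, the error is 1.5% to 6.8%.

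**The case against.** - **This is an abstract, and K-M is the natural estimator.** An abstract rarely gives an interval transformation, DFS is survival-time data, and the Z test stands in a row about planning. On that reading the Z error belongs to a test nobody intends to run. This largely stands as to the estimator, and the lower-limit rule is implied. It does not close the gap: the interval type is still open, and untransformed K-M limits have about the same excess error. Nor does the text say that the Z test is for planning only.
- **The disagreement is narrow.** At n = 114 it occurs only at exactly 4 events (probability 0.116 at DFS 0.98). That is true, but few events are expected, so this is a likely region.
- **A two-sample reading might hold the error.** It might if the reference sample is very small. The documents give no size.
- **The basis of 182.** A reader might infer that it came from an exact binomial test, since 114 has 80.5% exact power and inflates to 127 and then 182. The documents do not support this. The smallest n with 80% exact power is 107 (power 0.833), which inflates to 119 and then 170; 114 is reached only by working back from 182.
- **Sidedness and timing.** A reader might see a conflict between one-sided 0.025 and two-sided 0.05, but both give the same lower limit. A reader might also infer that the method will be picked after the data are seen. The documents leave that possible but do not show it.

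**Conclusion.** Wrong as written. The one non-inferiority test named does not hold its stated 2.5% when used one-sample against 0.92: the true error is 4.5% at n = 114 and about 6% on average. K-M with untransformed limits does no better. The stated test and inputs also do not give 182. The documents do not show which calculation did, and nothing should be inferred about its origin.

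The binomial figures rest on the stated 30% and 10% losses only; the K-M figures also rest on assumed exponential event and dropout times. The Withdrawal Criteria row lists further exclusions without rates, which would lower the evaluable number. The finding is conditional: it describes what happens if the named test, or K-M with untransformed limits, decides the primary comparison. It does not say that the trial will use either.

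**What to change.** 1. State that the unpooled Z test is for planning and is not the final test.
2. Print the decision rule: non-inferiority is declared only if the lower limit of the two-sided 95% interval for 3-year DFS exceeds 0.92.
3. Name one construction before data review.
   - **K-M at 3 years with complementary log-log limits.** With no events, use the exact lower limit 0.025^(1/m), where m is the number followed to 3 years; it exceeds 0.92 when m is at least 45.
   - **An exact binomial test at one-sided 0.025,** if the endpoint is analysed as a proportion, with a stated rule for patients lost before 3 years. At the full 0.025 it passes with at most 2 events for 100 to 106 evaluable, 3 for 107 to 124 and 4 for 125 to 142.
4. Say whether the planned interim analysis tests DFS. If it does, adjust the final level; the cut-offs and the no-event limit in item 3 would then change.
5. Restate the calculation behind 182 and the power so that both match the chosen test.

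**Cost.** Enrolment does not change. Average power at DFS 0.98 with 182 enrolled is about 79% (exact) or 77% (log-log K-M), against the stated 80% and about 94% for the Z test. That shortfall should be stated openly. If withdrawals removed an assumed further 5% or 10%, power would be 76% or 72% (exact) and 72% or 67% (log-log K-M). Any final level below 0.025 would lower it further.

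### The sample size of 182 does not follow from the inputs stated for it, and the unpooled Z test named there would not hold one-sided 2.5% as a final single-arm test

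*Combined protocol and SAP*

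**What the plan says.** All of this is in the Abstract of the combined protocol and SAP.

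- **Determination of Sample Size, benchmark and margin:** "The reference group proportion is 0.9800 according to the 3-year disease free survival rate reported in the previous literature"; and, with a minus sign in front, "0.06 is set to detect a non-inferiority margin". Together they imply a lower bound of 0.98 - 0.06 = 0.92.
- **Same row, test:** "The test statistic used is the one-sided Z test (unpooled). The significance level of the test is 0.025. The target Power is 0.80".
- **Same row, allowances:** "The inconsistency rate between preoperative and postoperative pathological diagnosis of GIST from literature is about 30" per cent, and "The dropout rate during follow-up is assumed to be 10" per cent.
- **Same row, result:** "The sample size needed by the study group was 182".
- **Research Design:** "Prospective, multicenter, open-label, single-arm".
- **Statistical considerations:** "The efficacy will be tested for non-inferiority with historical comparison". This row sets two-sided testing at 0.05 (the same 0.025 in the relevant tail), 95% confidence intervals and Kaplan-Meier (K-M) analysis of survival times. It does not name the test or the type of interval for the primary comparison.

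No row gives the assumed study-group DFS, the size of any reference group, an allocation ratio, the evaluable number before inflation, or the inflation formula.

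**The concern.** A non-inferiority sample size depends heavily on the true rate assumed in the study group, and that rate is missing. The paragraph also speaks of a reference group and an unpooled variance, which is the language of a two-group comparison, whereas the design has one arm and a historical value. Whether 0.98 is a fixed number or an estimate from a sample of known size changes the required number substantially.

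Two things are at stake. Without the assumed DFS and the form of the test, a reader cannot tell what power 182 delivers. And if the named Z test is carried into the final analysis of one arm, it could declare non-inferiority on data whose exact 95% lower limit lies below 0.92.

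**Working it through.** **Inputs from the sample size paragraph:** reference 0.98; margin 0.06; one-sided 0.025; power 0.80; retention 0.70 x 0.90 = 0.63. **Assumption where the plan is silent:** study-group DFS 0.98 unless another value is shown.

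**Step 1. Attempt to reproduce 182.** K = (1.96 + 0.8416)^2 = 7.849.

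- One sample against fixed 0.92: K x 0.98 x 0.02 / 0.06^2 = 42.7, so 43 evaluable; 43 / 0.63 = 68.3, so 69 enrolled.
- Two equal groups, 0.98 in both: K x 2 x 0.98 x 0.02 / 0.06^2 = 85.5, so 86 evaluable per arm; 86 / 0.63 = 136.5, so 137 enrolled per arm.

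Neither gives 182.

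**Step 2. What would give 182?** Two examples, both in the two-equal-group formula:

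- Study-group DFS 0.975, 80% power: K x (0.975 x 0.025 + 0.98 x 0.02) / 0.055^2 = 114.1; 114.1 / 0.63 = 181.1, so 182.
- DFS 0.98 in both groups, 90% power: (1.96 + 1.2816)^2 x 0.0392 / 0.0036 = 114.4; 114.4 / 0.63 = 181.6, so 182.

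The first needs an input that the plan does not state; the second needs a power that differs from the stated 0.80. The documents do not show which route, if either, was used.

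**Step 3. Error of the unpooled Z in one arm.** Assume that it is the final test, that 0.92 is fixed, and that every evaluable patient has known 3-year status. Evaluable number: 182 x 0.70 x 0.90 = 114.66, taken as 114.

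- 4 events: DFS 110/114 = 0.9649, SE = sqrt(0.9649 x 0.0351 / 114) = 0.0172, z = (0.9649 - 0.92) / 0.0172 = 2.61, which passes 1.96.
- 5 events: z = 1.88, which fails.
- True one-sided error: P(4 or fewer events, n = 114, event rate 0.08) = 4.5%.
- Over 107 to 124 evaluable, the error runs from 4.0% (at 116) to 8.6% (at 117). It is above 2.5% at every n from 40 to 182.

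At 4 events in 114 the exact (Clopper-Pearson) 95% lower limit is 91.3%, below 92%; at 3 events it is 92.5%. Exactly 4 events in 114 has probability 12% if true DFS is 0.98 and 19% if it is 0.96, so the two rules could well disagree.

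**Step 4. What 182 delivers with an exact binomial test against 0.92.**

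| Evaluable | Events allowed | True error | Power, DFS 0.98 | Power, DFS 0.975 |
|---|---|---|---|---|
| 106 | 2 | 0.8% | 64% | 50% |
| 107 | 3 | 2.5% (0.0245) | 83% | 72% |
| 114 | 3 | 1.6% | 80.5% | 68% |
| 124 | 3 | 0.9% | 76% | 62% |
| 125 | 4 | 2.5% (0.0248) | 89% | 80% |

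The figure of 106 is not remote. With 35% diagnostic inconsistency instead of about 30%, 182 x 0.65 x 0.90 = 106.5. If each of the 182 is independently evaluable with probability 0.63 (an assumption), the chance of 106 or fewer is about 11%.

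**The case against.** The strongest reply is that nothing here proves an error. The number can be reached by reasonable routes, and an unreported assumption is not a wrong one. That stands: this is incomplete reporting, and the stated inputs are not shown to contradict each other.

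A second reply is that the unpooled Z appears only in the sizing paragraph. Statistical considerations does not name it for the analysis, so the 4.5% may describe a test that will never be run. That also stands, and the error claim is therefore conditional. It still matters, because no other primary test is named.

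A third reply is that the exact test is a choice made here, whereas the plan foresees K-M, so the 80.5% partly reflects that choice. This is fair. With a log-log K-M limit and no censoring, 3 events clear 0.92 only from 114 evaluable, and power at DFS 0.98 is 64% to 61% over 107 to 113 even if zero events count as success. The remedy should therefore leave the choice of a valid test to the sponsor.

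A reader might also infer a one-sample calculation with study-group DFS 0.967, which reaches 182 by stepwise rounding (114, 163, 182) and would imply only 48% exact power. That value appears nowhere in the documents and was obtained by solving backwards. It should not be used as evidence of low power.

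**Conclusion.** The point holds in this form. The 182 does not follow from the stated inputs: with study-group DFS at 0.98 they give 69 enrolled for one sample or 137 per arm for two equal groups, and the missing or different input cannot be identified. The test wording does not match a single-arm design. The error of 4.5% at 114 evaluable (4.0% to 8.6% over 107 to 124), against the stated 2.5%, rests on three assumptions: the Z is the final test, 0.92 is fixed, and 3-year status is complete.

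A reader might conclude that 182 is too small. The documents do not support that: with an exact one-arm test and true DFS 0.98, the planned 114 evaluable patients give 80.5% power. That figure is sensitive to the true DFS and to losing only a few more patients than planned. The sponsor should settle this before the primary analysis. How alpha is handled at the planned interim analysis is a separate point.

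**What to change.** Keep 182 and amend the wording.

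1. State the calculation actually used: assumed study-group DFS, power, whether the reference is fixed or sampled (and its size), evaluable number and inflation steps. If 90% power was used, correct the stated 0.80.
2. State that 98% is a fixed historical value and that 3-year DFS is tested against 0.92 with a one-arm test that holds one-sided 0.025. One option is an exact binomial test, with success if the lower limit of the two-sided 95% exact interval exceeds 0.92.
3. Restate the power for that test, labelled as a restated justification of the existing number and without a selective range. For the exact test at 114 evaluable: success at 3 or fewer events, true error 1.6%, power 80.5% at DFS 0.98 and 68% at 0.975. At DFS 0.98, power is 83% at 107 and 76% at 124, but 64% at 106 and 89% at 125.
4. If a K-M limit is preferred, to match Statistical considerations, name it and recompute error and power for that limit.

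**Cost:** protocol and SAP text only, with no change to enrolment. The downsides are that the restated power depends on the final evaluable number and can fall to about 64% if slightly more patients are lost than planned. The exact test also uses only patients with known 3-year status, so K-M would remain as the supportive analysis.

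### Withdrawal for spontaneous rupture found at operation needs no proof that it preceded tumour handling, and the analysis of withdrawn patients is not stated

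*Combined protocol and SAP*

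**What the plan says.** All references are to the Abstract of the combined protocol and SAP, which is the only part supplied.

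- **Research Design:** "Prospective, multicenter, open-label, single-arm", at 13 centres. The stated purpose is to evaluate the safety of the laparoscopic technique.
- **Withdrawal Criteria:** one item reads "Patients confirmed as spontaneous tumor rupture, metastasis or invading nearby organs intraoperately". Rupture is the only one of the three findings qualified by its cause. No definition, evidence of timing, named assessor or independent confirmation is given.
- **Endpoints:** the primary endpoint is 3-year DFS. A secondary endpoint is "Rate of intraoperative complication", with no list of what counts.
- **Determination of Sample Size:** "The reference group proportion is 0.9800 according to the 3-year disease free survival rate reported in the previous literature", and the margin is given as "0.06 is set to detect a non-inferiority margin" (with a minus sign), so the bound is 0.98 - 0.06 = 0.92. The source is described as "previous literature on the subject of gastric GIST with maximum diameter between 2 to 5cm". Allowances of 30% for pathology mismatch and 10% for dropout are included.
- **Statistical considerations:** non-inferiority against a historical rate, with Kaplan-Meier and Cox methods. No analysis set is named, and nothing is said about follow-up or analysis of withdrawn patients.

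**The concern.** Rupture during handling is a harm that the studied technique could itself produce. Whether a rupture was already there or arose during dissection is judged once the operation is under way, by people who know the treatment and the aim of the trial. Withdrawal on that judgement is selection after the intervention has begun, unless the timing is documented independently of the judgement. Metastasis and invasion are also discovered at operation, but the surgeon does not plausibly cause them. With rupture, the reason for withdrawal and the effect of the intervention can be confused.

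If a withdrawn patient also leaves the analysis, calling a doubtful rupture spontaneous removes a possible complication and, if the patient later relapses, a DFS event. With a reference event rate of 2%, a few events settle the primary conclusion. There is no concurrent arm in which the same rule would operate.

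**Working it through.** **1. Inputs.** From the plan: sample size 182, reference 0.98, margin 0.06, one-sided alpha 0.025, power 0.80, losses of 30% and 10%. Not in the plan, and assumed below: the number of ruptures, their relapse risk, and a one-sample binomial analysis in place of Kaplan-Meier.

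**2. The plan's own figure.** The formula behind 182 cannot be identified from the text.
- Two-sample unpooled Z: 2 x 0.98 x 0.02 x (1.960 + 0.842)² / 0.06² = 85.5, so 86; 86/0.7 gives 123; 123/0.9 gives 137.
- One-sample Z with null variance at 0.92: (1.960 x √(0.92 x 0.08) + 0.842 x √(0.98 x 0.02))² / 0.06² = 117.2, so 118; then 169; then 188.
- One-sample exact binomial: power is at least 0.80 for n = 107 to 115. Within that range n = 114 gives 163, then 182, although the smallest n, 107, gives 170.

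I take 182 as given; the point does not depend on how it was derived.

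**3. Evaluable patients.** 182 x 0.7 x 0.9 = 114.7, about 115.

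**4. Events allowed against 0.92.** Two-sided 95% lower limits (2.5% in the lower tail):

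| Events/n | Exact (Clopper-Pearson) | Wald, p - 1.96√(p(1-p)/n) |
|---|---|---|
| 3/115 | 0.926, pass | 0.945, pass |
| 4/115 | 0.913, fail | 0.932, pass |
| 5/115 | 0.902, fail | 0.919, fail |

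The allowance is 3 events with the exact limit and 4 with the Wald limit.

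**5. One patient at the boundary.** Removing one relapsing patient turns 4/115 (fail) into 3/114 (exact limit 0.925, pass). With the Wald limit it turns 5/115 (fail) into 4/114 (0.931, pass). Either way one patient reverses the verdict.

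**6. Illustration: two ruptured patients kept instead of withdrawn.** Let r be their relapse risk (assumed 25% or 50%) and F(k) the chance of at most k events among the other 115. With the exact limit, 3 events are still allowed at n = 117, so the chance of success is (1-r)²F(3) + 2r(1-r)F(2) + r²F(1).
- True DFS in the others 0.98: F(3), F(2), F(1) = 0.801, 0.595, 0.328. With the two withdrawn: 0.80. Kept, r = 25%: 0.5625 x 0.801 + 0.375 x 0.595 + 0.0625 x 0.328 = 0.69. Kept, r = 50%: 0.25 x 0.801 + 0.5 x 0.595 + 0.25 x 0.328 = 0.58.
- True DFS in the others 0.97 (assumed): F = 0.546, 0.326, 0.137. Withdrawn: 0.55. Kept: 0.44 (25%) or 0.33 (50%), by the same formula.

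These falls belong to the exact limit. With the Wald limit, 5/117 has a lower limit of 0.921 and passes, so the allowance rises from 4 to 5. At 0.98, F(5) = 0.972 and F(4) = 0.918, and the chance goes from 0.92 to 0.5625 x 0.972 + 0.375 x 0.918 + 0.0625 x 0.801 = 0.94 (25%), or 0.25 x 0.972 + 0.5 x 0.918 + 0.25 x 0.801 = 0.90 (50%). The average effect therefore depends heavily on the test; the sensitivity to single patients in step 5 does not.

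**The case against.** The criterion is limited to spontaneous rupture and stands beside metastasis and invasion, which are disease states that precede surgery. Read that way, it removes patients outside the target population and leaves technique-related rupture in. Withdrawing a rupture that truly predates surgery is defensible, and then it introduces no bias. This stands. What it does not supply is any means of telling the two kinds of rupture apart.

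The strongest objection is that withdrawal is not the same as leaving the analysis. A reader might infer that the label decides who counts in DFS and in the complication rate. The documents do not say so. The 30% pathology allowance suggests that non-GIST patients are treated as not evaluable, but nothing equivalent is said about rupture.

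Several other inferences are tempting and also lack support:
- that the operator assigns the label (no assessor is named);
- that surgeon-caused rupture counts as a complication (the endpoint is not defined);
- that ruptured patients are those most likely to relapse (no relapse risk is given);
- that ruptures in these elective patients are often of uncertain origin (the exclusion of emergency surgery does not show this);
- that misattribution can only flatter the technique (a spontaneous rupture recorded as surgical errs the other way);
- that the 0.98 source kept ruptured tumours in (it is summarised in one phrase).

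Finally, only the abstract is available, and a fuller protocol may define these terms.

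**Conclusion.** The concern holds in a limited form. The withdrawal rule rests on an unblinded judgement of cause, made after the intervention has begun, with no required evidence of timing, and the plan does not state how withdrawn patients are analysed. If they leave the denominators, bias towards non-inferiority is possible. If they stay in, the effect is zero.

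The firm quantitative finding is fragility: with about 115 evaluable patients and 3 or 4 allowable events, one or two patients can decide the primary conclusion. This rests on the plan's own losses and on a binomial approximation.

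The drop in success chance (0.80 to 0.69-0.58 at a true DFS of 0.98, or 0.55 to 0.44-0.33 at 0.97) is illustrative only. It assumes an exact limit, two ruptures and relapse risks of 25-50%, none of which the plan gives, and it measures bias only for ruptures that were not truly spontaneous. A reader might take it as evidence that the trial's result will be biased; the documents do not support that. The point merits an amendment but does not invalidate the design.

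**What to change.** 1. For analysis purposes, accept a rupture as spontaneous only if it is documented on preoperative imaging or at first inspection before the tumour is handled.
2. Analyse every other rupture as intraoperative: count it in the intraoperative complication rate and keep the patient in 3-year DFS.
3. State whether patients meeting each withdrawal criterion stay in the DFS and complication denominators.
4. Follow up all ruptured GIST patients for DFS, and report a sensitivity analysis that includes all of them.

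Cost: an amended definition, one CRF field for when and how the rupture was first seen, and continued follow-up of any such patients. The downside is that some truly spontaneous ruptures without documentation may count against the technique, making the DFS and complication figures slightly less favourable.

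### With 13 centres and only about 2 to 10 expected DFS events, must the plan fix the form and status of its optional Cox centre analysis?

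*Combined protocol and SAP*

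**What the plan says.** All the relevant text is in the Abstract table of the combined protocol and SAP.

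- **Research Design:** the trial is "Prospective, multicenter, open-label, single-arm". **Number of Research Centers** gives 13.
- **Determination of Sample Size:** "The reference group proportion is 0.9800 according to the 3-year disease free survival rate reported in the previous literature". The margin is 0.06, and the test is a one-sided unpooled Z test at 0.025 with 80% power. The losses are about 30% for a pathology result that contradicts the preoperative diagnosis and 10% for dropout. The study group is 182.
- **Withdrawal Criteria:** patients found not to have GIST on postoperative pathology leave the study.
- **Statistical considerations, primary comparison:** "The efficacy will be tested for non-inferiority with historical comparison". Kaplan-Meier and Cox methods are both listed for survival times.
- **Statistical considerations, centre effects:** a mixed model is named for quantitative measures, CMH for qualitative ones and a hierarchical logistic model for grades. Then "survival time variables will be evaluated and adjusted using a Cox regression model". The condition attached is: "The central effect analysis and subgroup analysis will be carried out according to the specific situation".

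The text does not give the form of the centre term in the Cox model (fixed, stratified or random). It has no rule for pooling small centres and no label of supportive or sensitivity analysis. No sentence states outright that the DFS compared with the historical rate is unadjusted for centre.

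**The concern.** The primary endpoint, 3-year DFS, is a survival-time variable, so the Cox sentence covers it. The plan also expects very few DFS events. If centre were coded as 12 indicator terms, centres with no event would have no finite coefficient, and a DFS curve predicted from that fit would be unreliable. Stratifying by centre estimates no centre effect at all. A random centre effect stays finite but has almost nothing to estimate from.

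Two harms could follow. A centre-adjusted DFS might be reported beside the unadjusted one, with nothing to say which of them carries the conclusion. And a non-significant centre result, likely with so few events, might be taken as evidence that 13 surgical centres perform alike.

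**Working it through.** **Inputs** (Determination of Sample Size, Number of Research Centers): N = 182; losses 30% and 10%; reference DFS 0.98; margin 0.06; 13 centres. The limit is 0.98 − 0.06 = 0.92.

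**The plan's 182.** The unpooled two-group formula with (1.960 + 0.842)² = 7.849 gives 2 × 0.98 × 0.02 × 7.849 / 0.06² = 85.5, so 86 patients, and 86 / (0.7 × 0.9) = 137. That is not 182. An exact one-sample binomial test against 0.92 has power 0.80 at 115 patients, and 115 / 0.63 = 183, close to the stated figure. Which method was used is a separate matter. Here 182 is taken as given.

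**Evaluable patients.** 182 × 0.7 × 0.9 = 114.7, about 115. Dropouts still contribute censored follow-up to a Cox model, so 182 × 0.7 = 127.4, about 127, is also a fair count. All 182 is the most generous bound.

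**Expected events** = n × (1 − DFS). **Expected event-free centres** = sum over centres of DFS^(centre size). The plan gives no centre sizes. Equal sizes are assumed first, then a strongly unequal set (30, 20, 15, 10, 8, 7, 6, 5, 4, 4, 3, 2, 1).

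For 115 patients in equal centres (eleven of 9, two of 8):

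- DFS 0.98: 11 × 0.98⁹ + 2 × 0.98⁸ = 9.17 + 1.70 = 10.87
- DFS 0.92: 11 × 0.92⁹ + 2 × 0.92⁸ = 5.19 + 1.03 = 6.22

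| Patients and centre sizes | Events at 0.98 / 0.92 | Event-free centres at 0.98 / 0.92 |
|---|---|---|
| 115, equal | 2.3 / 9.2 | 10.9 / 6.2 |
| 115, unequal | 2.3 / 9.2 | 11.0 / 7.3 |
| 127, equal (ten of 10, three of 9) | 2.5 / 10.2 | 10.7 / 5.8 |
| 182, equal (14 each) | 3.6 / 14.6 | 9.8 / 4.0 |

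The chance of at least one event-free centre, 1 − product of (1 − DFS^size), is at least 0.9995 in the first three rows and 0.992 in the last at DFS 0.92. With 12 fixed terms and 115 patients there are 2.3 / 12 = 0.19 to 9.2 / 12 = 0.77 events per coefficient.

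So the sparse-data point holds whatever the denominator or enrolment pattern.

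**Does it reach the primary result?**

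1. The non-inferiority comparison with the historical rate is stated in its own sentence, apart from the centre analysis.
2. The test used to size the trial compares a 3-year proportion with 0.98 less 0.06. It contains no centre term.
3. A single-arm Cox model has no treatment coefficient. Adding centre gives hazard ratios between centres, and it does not directly test a 3-year rate against 0.92.
4. The centre analysis depends on circumstances, so it may be left out when events are too few.

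The natural reading is therefore an unadjusted 3-year DFS for the test, with any Cox centre model beside it as description.

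**The case for a change.** The strongest case for a change is that the remedy costs a few sentences and one table, and that the documents leave real gaps. The plan gives no criterion for doing or omitting the centre analysis, so that choice could follow sight of the data. The Z test appears only in the sample-size text. Statistical considerations asks instead for two-sided tests at 0.05 and lists both Kaplan-Meier and Cox without naming a primary method. The sparse-data arithmetic is also robust.

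The omissions and the arithmetic stand. The consequence is weaker than it looks:

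- **Fixed indicators are an assumption.** Only that coding fails outright. The same sentence names mixed and hierarchical models for other data types, so fixed terms are not the evident default.
- **The two-sided wording is no conflict here.** The lower limit of a two-sided 95% interval corresponds to a one-sided test at 0.025.
- **The misreading is hypothetical.** Nothing in the plan says that a non-significant centre term would be taken as agreement between centres.
- **One illustration fails.** If three events all fell in one centre of 9, a 12-df likelihood-ratio test would give 2 × [ln(115 × 114 × 113) − ln(9 × 8 × 7)] = 15.97, p = 0.19, as though extreme clustering would go unseen. That approximation is not valid with three events. With equal centres, the exact chance that three events share any one centre is (11 × 84 + 2 × 56) / 246,905 = 0.0042.
- **A prescribed model gains little.** A random centre effect stays finite, but in a simulation that approximated it with a gamma-Poisson model, the centre variance was estimated as zero in 79% (equal centres) or 67% (unequal) of trials at 98% DFS. Those percentages rest on assumed centre sizes, but they show that specifying the coding would not make the analysis informative.

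A table of patients and DFS events by centre would be useful. It is ordinary reporting that analysts can produce without a change to the plan.

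**Conclusion.** No change follows. A Cox centre analysis of DFS would carry little information: about 2 to 10 expected events and about 6 to 11 event-free centres out of 13, for 115 to 127 patients and DFS between 98% and 92%. Counting all 182 patients still leaves about 4 to 10 centres without an event. These counts assume that the planned losses occur and, apart from the unequal-size check, that enrolment is even.

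The missing form and status of this analysis are a gap that analysts would fill sensibly. They would test the unadjusted 3-year DFS, treat any centre model as supportive, and omit or simplify it when events are few. Stating this would leave the sample size, alpha, power, test and primary conclusion as they are. The verdict rests on reading the historical comparison as unadjusted, which the sample-size test and the single-arm design both support.
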